### **15.2 Demographic and Baseline Characteristics**

The following demographic variables at screening will be summarized: race, gender, age, primary antianxiety medication currently taking, and primary psychotherapy treatment currently participating in.

### **15.3 Analysis of Primary Endpoint**

The primary endpoints will be feasibility and acceptability of the Empower Neuromodulation System as a daily therapy for GAD. Feasibility will be evaluated via

treatment adherence, and acceptability will be evaluated via usability as assessed by the SUS questionnaire.

Feasibility: We will calculate adherence (treatment sessions administered as a percentage of total possible) for each participant. We will consider a treatment session to be completed if at least 20 minutes of the session was administered. We will also compare adherence between the active and sham treatment groups (t-test).

Acceptability: We will compare SUS scores for the active and sham treatment groups (t-test), and compare each against the average (SUS $\geq$ 68) and excellent (SUS $\geq$ 80) benchmarks.

#### 15.4 Analysis of Secondary Endpoints

Secondary endpoints will be analyzed via the methods described below. Unless otherwise noted, for daily and weekly metrics, we will use a random-intercept linear mixed model with restricted maximum likelihood to compare results between the active and sham treatment groups. As a secondary analysis for each of these endpoints, we will evaluate the correlations for duration since last benzodiazepine dose and dose amount vs. the endpoint. If this relationship is significant for an endpoint, we will include time since last dose in our statistical analysis.

Feasibility: Effective nerve stimulation: We will calculate effective nerve stimulation (treatment sessions that elicit skin tingling as a percentage of total treatment sessions) for each participant. We will also compare effective nerve stimulation between the active and sham treatment groups (t-test).

Acceptability: Overall satisfaction with treatment: We will compare overall satisfaction with treatment scores between the active and sham treatment groups (t-test).

Safety: We will tabulate AEs across all participants. This will include tabulating the number of participants for whom the event occurred, the rate of occurrence, and the severity and relationship to the study device.

Effectiveness: Change in HAM-A score: We will compare the change in HAM-A score between the active and sham treatment groups (t-test).

Effectiveness: Change in GAD-Q-IV score: We will compare the change in GAD-Q-IV score between the active and sham treatment groups (t-test).

Effectiveness: Change in BAI score: We will compare the change in BAI score between the active and sham treatment groups (mixed models).

Effectiveness: Change in daily anxiety severity self-report: We will compare the change in daily anxiety severity scores between the active and sham treatment groups (mixed models).

Effectiveness: Change in daily anxiety interference self-report: We will compare the change in daily anxiety interference scores between the active and sham treatment groups (mixed models).

Effectiveness: Change in anxiety severity self-report as an immediate result of treatment: We will compare the short-term effect of Empower treatment on anxiety severity score (% change for post-treatment score vs. pre-treatment score) (repeated measures ANOVA with Tukey correction, active vs. sham treatment group).

Effectiveness: Medication use: We will calculate average benzodiazepine use per week. We will compare medication use between the active and sham treatment groups (mixed models).

Effectiveness: Change in HAM-D score: We will compare the change in HAM-D score between the active and sham treatment groups (t-test).

Effectiveness: Change in PHQ-9 score: We will compare the change in PHQ-9 score between the active and sham treatment groups (t-test).

Effectiveness: Change in PCL-5 score: We will compare the change in PCL-5 score between the active and sham treatment groups (t-test).

Effectiveness: Change in PSQI score: We will compare the change in PSQI score between the active and sham treatment groups (t-test).

Effectiveness: Change in SF-12 score: We will compare the change in SF-12 score between the active and sham treatment groups (t-test).

Blinding: We will statistically assess blinding for the active and sham treatment groups using the blinding index from Bang et al.

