#### 3.2 Secondary Objectives

The secondary study objectives are the following:

- Feasibility: Evaluate the feasibility of the Empower Neuromodulation System treatment via its ability to provide effective nerve stimulation (via participant-reported tingling sensation, a direct indication of effective nerve stimulation)
- Acceptability: Evaluate the acceptability of the Empower Neuromodulation System treatment via overall satisfaction with treatment (via 100-mm VAS)
- Safety: Evaluate the safety of the Empower Neuromodulation System treatment via device-related adverse events
- Effectiveness: Evaluate the effectiveness of the Empower Neuromodulation System treatment for (all endpoints assessed for active vs. sham groups):
  - Reducing clinician-assessed anxiety severity (via Hamilton Anxiety Rating Scale (HAM-A))
  - Reducing participant-reported anxiety severity (via Beck Anxiety Inventory (BAI), Generalized Anxiety Disorder Questionnaire-IV (GAD-Q-IV), daily self-reports for anxiety severity (100-mm VAS), and pre- and post-treatment self-reports of anxiety severity (100-mm VAS))
  - Reducing participant-reported anxiety interference with daily living (via daily self-reports for anxiety interference with daily living (via 100-mm VAS))
  - Reducing medication use (via self-reports)
  - Reducing clinician-assessed depression severity (via Hamilton Depression Rating Scale (HAM-D))
  - Reducing participant-reported depression severity (via Patient Health Questionnaire-9 (PHQ-9))
  - Reducing participant-reported post-traumatic stress disorder (PTSD) severity (via PTSD Checklist-5 (PCL-5))
  - Improving sleep quality (via Pittsburg Sleep Quality Index (PSQI) survey)
  - Improving quality of life (via SF-12 survey)
- Blinding: Evaluate if the active and sham treatments are well-blinded per the blinding assessment

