### 5.2 Secondary Endpoints

The following secondary endpoints will be evaluated:

- Feasibility: For each treatment group, the percentage of treatment sessions that provide effective nerve stimulation as assessed via participant-reported confirmation of tingling sensation
- Acceptability: For each treatment group, the overall satisfaction with treatment (via 100-mm VAS)
- Effectiveness:
  - Effect of treatment group on change in clinician-assessed anxiety severity (via HAM-A)
  - Effect of treatment group on change in weekly participant-reported anxiety severity (via BAI)
  - Effect of treatment group on change in participant-reported GAD symptoms (via GAD-Q-IV)
  - Effect of treatment group on change in daily self-reports for anxiety severity (via 100-mm VAS)
  - Effect of treatment group on change in self-reports of anxiety severity immediately after vs. before treatment (via 100-mm VAS)
  - Effect of treatment group on change in daily self-reports for anxiety interference with daily living (via 100-mm VAS)
  - Effect of treatment group on medication use (via self-reports)
  - Effect of treatment group on change in clinician-assessed depression severity (via HAM-D)
  - Effect of treatment group on change in participant-reported depression severity (via PHQ-9)
  - Effect of treatment group on change in participant-reported PTSD severity (via PCL-5)
  - Effect of treatment group on change in sleep quality (via PSQI survey)

- Effect of treatment group on change in quality of life (via SF-12 survey)
- Blinding: For each treatment group, the blinding index and 95% confidence interval (via Bang et al. blinding assessment method)

All of these secondary endpoints provide valuable information on the effectiveness of the Empower Neuromodulation System for GAD treatment as well as the acceptability to the intended patient population.

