### 6.3 Exclusion Criteria

1. Has current (past 30 days) psychotic or bipolar disorder, homicidal ideation, psychiatric hospitalization, or moderate/severe SUDs per clinician assessment via M.I.N.I.
2. HAM-D  $\geq 18$
3. PCL-5  $\geq 34$
4. Exhibits suicidal intent as confirmed on the Columbia-Suicide Severity Rating Scale-Revised (C-SSRS-R) with a “Yes” response to question 4 or question 5, or to question 6 in the past 3 months.
5. Changes in psychoactive medications in the past 30 days (including but not limited to psychotropic medications, thyroid hormone medication, steroids), with the exception of benzodiazepines
6. If regularly taking benzodiazepines, has had changes in benzodiazepine dosing in the past 30 days or average use  $> 2$  days per week
7. Psychotherapy was initiated or discontinued in the past 30 days or psychotherapy modality was changes in the past 30 days
8. Has a history of epilepsy or a seizure disorder

9. Has been diagnosed with peripheral nerve damage of the arm or hand or has numbness or tingling in the arm or hand at least weekly
10. Is currently pregnant or breastfeeding, has been pregnant within the past 6 months or intends to become pregnant during the study period
11. Currently has an active implant and/or an electrical or neurostimulator device, including but not limited to cardiac pacemaker or defibrillator, vagal neurostimulator, deep brain stimulator, spinal stimulator, sacral stimulator, bone growth stimulator, or cochlear implant
12. Has an electrically conductive metal object (e.g. jewelry) that cannot be removed from [REDACTED] and will directly contact the gel electrodes of the Empower Neuromodulation System at either anatomic location
13. Has an open incision, wound, scar, active infection or otherwise compromised skin at the [REDACTED] and will directly contact the gel electrodes of the Empower Neuromodulation System at either anatomic location
14. Does not have daily access to an electrical outlet for charging the investigational device and associated smartphone
15. Has used of an investigational drug/device therapy within the past four weeks
16. Unable to provide informed written consent
17. Has any medical condition that would, in the opinion of the investigator, make the participant ineligible

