#### ***9.1.7.1 Daily Surveys***

The daily survey questions will be completed on the Empower app and include questions about non-scheduled anxiety medication use (e.g. benzodiazepine dose taken over the past 24 hours and day/time of last dose), anxiety severity over the past 24 hours, anxiety interference with daily life over the past 24 hours, and anxiety severity at the present time. For anxiety severity, the participant will be asked to rate it on a 100-point visual analog scale (VAS) [0="No anxiety at all" through 100="Severe Anxiety"]. For anxiety interference with daily life, the participant will be asked to rate it on a 100-point visual analog scale (VAS) [0="Not at all" through 100="Extreme"].

The app will guide the participant to complete the daily survey prior to self-administering the first treatment session of each calendar day. Immediately after the session, the participant will also be asked about anxiety severity at the present time and if a tingling sensation was felt on the skin at the site of stimulation application to confirm effective nerve stimulation.

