## 10 EVALUATIONS BY VISIT

### 10.1 Visit 1 (Day 1)

1. Review the study with the participant and obtain written informed consent and HIPAA authorization and assent
2. Assign the participant a unique screening number
3. Record demographics data
4. Record medical history
5. Record concomitant medications
6. Perform an abbreviated physical examination
7. Perform an abbreviated psychiatric examination, including M.I.N.I. and C-SSRS-R
8. Collect urine sample and perform a urine pregnancy test, if applicable
9. Perform clinician-administered assessments (HAM-A and HAM-D) and participant-reported survey (PCL-5)
10. Final review of eligibility
11. Complete self-report surveys (GAD-Q-IV, PHQ-9, PSQI, SF-12)
12. Randomize participant
13. Train participant on Empower device, smartphone, and app.
14. Self-administer a treatment session and complete app-based surveys (BAI, medication use, anxiety severity and interference, skin tingling)
15. Record adverse events, if applicable
16. Schedule participant for Visit 2 in 14 days

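### The benzodiazepine-adjustment rule in Section 15.4 would adjust weekly benzodiazepine use for its own dosing record, and does not say whether the adjusted model replaces or accompanies the model stated first

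*Combined protocol and SAP*

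**What the plan says.** Section 15.4 compares active and sham on daily and weekly metrics with a random-intercept linear mixed model fitted by REML. No benzodiazepine term is listed. It continues: "As a secondary analysis for each of these endpoints, we will evaluate the correlations for duration since last benzodiazepine dose and dose amount" against the endpoint, and then: "If this relationship is significant for an endpoint, we will include time since last dose in our statistical analysis".

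The endpoints that Section 15.4 assigns to mixed models are BAI, daily anxiety severity, daily anxiety interference and medication use. On medication use the section says: "We will calculate average benzodiazepine use per week. We will compare medication use between the active and sham treatment groups (mixed models"). Nothing exempts that endpoint from the rule.

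Both the outcome and the covariate come from the daily app survey in Section 9.1.7.1, which asks for "benzodiazepine dose taken over the past 24 hours and day/time of last dose". Section 10.1 places the first app survey at step 14 of Visit 1, after randomisation at step 12. Sections 3.2 and 5.2 list medication use as an outcome of treatment group.

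**The concern.** There are three difficulties.

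- **Role.** The text does not say which model carries the active-versus-sham conclusion once the trigger fires.
- **Circularity.** If weekly benzodiazepine use is adjusted for time since last dose, the comparison conditions on the same dosing events that it is meant to compare.
- **Post-randomisation covariate.** Apart from the Day 1 answer, which precedes the first session, every report of time since last dose is made on treatment. If the device changes dosing and dosing is linked to anxiety, the adjusted anxiety estimate is no longer the total effect of treatment.

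The rule is also incomplete. It does not say whether a significant dose-amount correlation alone triggers it, what correlation method or significance level applies, or which time-since-dose value belongs to a week. It gives no value for a participant with no dose, although nothing in Sections 6.2, 6.3 or 7.1 requires benzodiazepine use.

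At stake are the estimates for four of the twelve effectiveness endpoints. Section 5.1 looks ahead to a pivotal study, so the size of these pilot estimates matters as well as their p-values.

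**Working it through.** The plan gives no figure for this rule, and its sample size (2 × 15 = 30) rests on precedent, so there is no plan calculation to reproduce. Every dosing input below is an assumption. The documents give neither the share of users nor any device effect on dosing.

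**1. The mechanical link.** Suppose a participant doses on any day with constant probability p. Long-run dosing days per week are 7p, and mean days since last dose (0 on a dosing day) are (1 − p)/p.

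- Sham, p = 0.25: 7 × 0.25 = 1.75 days/week; 0.75/0.25 = 3.0 days since dose.
- Active, p = 0.125: 7 × 0.125 = 0.875 days/week; 0.875/0.125 = 7.0 days since dose.

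The arm difference of 0.875 − 1.75 = −0.875 days/week necessarily moves the covariate as well, from 3.0 to 7.0 days.

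**2. Simulation at those probabilities** (six weeks, REML random-intercept model, weekly-mean time since dose, 300 runs).

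- 15 users per arm: correlation about −0.58; screen significant in 100% of runs; arm effect −0.884 unadjusted and −0.505 adjusted. Share removed = 1 − 0.505/0.884 = 43%.
- 8 users per arm: −0.858 to −0.479; 1 − 0.479/0.858 = 44%.
- No treatment effect: the screen was still significant in 100% of runs.

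**3. Simulation with an entry cap of 2 dosing days/week** (15 per arm, dosing odds halved on active, 1,000 runs, non-users kept with a user indicator). In each cell the first value is for dosing unrelated to anxiety and the second for dosing that tracks anxiety.

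| Users | Unadjusted, days/week | Adjusted, weekly-mean or end-of-week value | Removed |
|---|---|---|---|
| 100% | −0.67 / −0.52 | −0.31 to −0.34 / −0.27 to −0.32 | 49–54% / 38–48% |
| 70% | −0.46 / −0.37 | −0.21 to −0.23 / −0.19 to −0.22 | 50–54% / 41–49% |
| 40% | −0.27 / −0.21 | −0.11 to −0.12 / −0.10 to −0.11 | 56–59% / 48–52% |

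With these codings the trigger fired in at least 99.9% of runs. With the first-day-of-week value only 9% to 15% was removed, and the trigger fired in 42% to 97% of runs.

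**4. Non-users coded 0, no user indicator** (weekly mean, dosing unrelated to anxiety).

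- 70% users: −0.43 to −0.31; 1 − 0.31/0.43 = 28%.
- 40% users: −0.23 to −0.17; 1 − 0.17/0.23 = 26%.

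A further set of runs across codings removed about 4% to 45%. The direction is the same throughout; the amount depends on choices that the plan leaves open.

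**5. Daily anxiety on the 100-point VAS** (device effect −10 apart from any change in dosing; all participants users; total effect against adjusted estimate, with time since dose entered as linear days or as log2).

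- Dosing only tracks anxiety: −10.0 against −8.8 or −7.9.
- A recent dose relieves anxiety, dosing unrelated to anxiety: −8.0 against −9.9 or −10.0.
- Both links: −6.6 against −8.3 or −7.9.
- Dosing and anxiety unrelated, or dosing unchanged by the device: no shift.

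The largest shift is 10.0 − 7.9 = 2.1 points. Against an SE of 3.7 that is 2.1/3.7 = 0.57 SE. At 40% users the largest shift (linear days) is 9.9 − 9.2 = 0.7 points.

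**6. Dropping non-users.** At 40% users, omitting participants with no time-since-dose value raised the SE of the daily VAS difference from 4.6 to 7.7. This is a consequence of the missing coding rule.

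**Limits.** The simulations use dosing days and an arm main effect on levels, and those in steps 3 and 5 take the trigger as a pooled Pearson p < 0.05. The plan speaks of average use and of change in scores, and names no correlation method.

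**The case against.** The strongest reply is that Section 15.4 states the main comparison first and opens the benzodiazepine step as a secondary analysis. The conditional sentence follows directly and can be read as part of that step. On that reading the main estimates stand. This is a fair reading and perhaps the more natural one, but the text does not settle it. It also does not rescue medication use: an adjusted comparison of weekly use is not informative about the treatment effect even as a supplement.

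Other points stand in part.

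- Time since last dose is not an exact function of weekly use. The two are mechanically and inversely related through the same reports, which is enough for the problem.
- The percentages depend on the coding of time since dose and of non-users, so no single figure should be quoted.
- Section 7 asks for stable psychoactive medication where medically feasible, which may limit changes in dosing. But the plan makes medication use an effectiveness outcome, so it allows that use may differ by arm.
- These are secondary endpoints of a 30-person pilot. That limits the severity.

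A reader might go further and infer that the rule inflates type I error, or that it lowers power generally. Neither is supported. With the device lowering dosing but not anxiety, daily VAS rejection was 0.048 unadjusted against 0.055 or 0.067 adjusted (Monte Carlo SE about 0.007), too little to claim inflation. Power comparisons depend on the share of users and on whether a user indicator is in both models, so no general loss can be stated.

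**Conclusion.** For medication use the rule is wrong as written, whichever role the adjusted model has. The trigger fires almost always when time since dose is summarised over the week or taken at its end, and the adjustment then removes part of the difference under test. Under assumed dosing the share removed runs from under 15% (first-day value) to roughly 25% to 59% (weekly-mean or end-of-week value), and lower in some runs with non-users coded 0 and no indicator. These are illustrations, not predictions.

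For BAI, daily severity and daily interference, the point is an unstated role and a post-randomisation covariate. The adjusted estimate departs from the total effect only if the device changes dosing and dosing is linked to anxiety. The simulated shift is at most about 0.6 SE, in either direction.

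One might read the plan as replacing the main model, or as certain to halve any benefit on benzodiazepine use. The documents establish neither. Adherence, SUS and the endpoints that Section 15.4 assigns to t-tests, such as HAM-A, are not affected on the natural reading, although the scope of the rule could be read more widely. This should be fixed before unblinded analysis; it does not threaten the primary objectives.

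**What to change.** Amend Section 15.4 as follows.

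1. State that the mixed model without any benzodiazepine variable recorded after randomisation is the main active-versus-sham analysis for BAI, daily severity, daily interference and medication use.
2. Remove the significance trigger from that comparison.
3. State that medication use is never adjusted for time since last dose or dose amount.
4. Report the associations of time since dose and dose amount with the anxiety endpoints as exploratory, using a method that accounts for repeated measures, with a stated coding for participants with no dose.

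Adjustment for benzodiazepine use recorded at Screening (Section 9.1.1) is optional. If wanted, it should be prespecified, with 0 for non-users. Its gain depends on how accurately that use is recorded, since Screening takes a medication history and not a dosing log.

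The cost is SAP wording, with no new data. The daily anxiety estimates lose a little precision where dosing tracks anxiety (all users: SE 3.7 without time since dose, 3.3 to 3.5 with it) and none where it does not (4.5 in both).

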### 4.4 Study Overview

This is a single site, sham-controlled, double-blinded trial. The overall study goal is to evaluate the feasibility and acceptability of the Empower Neuromodulation System as a daily therapy for GAD patients. The total duration of participant participation will be six weeks (**Fig. 2**), and the total duration of the study is expected to be 9 months. Screening data will be reviewed to determine participant eligibility. Participants who meet all of the inclusion criteria and none of the exclusion criteria will be eligible to be randomized.

At enrollment, participants will be randomized (1:1) to either the active treatment arm [REDACTED] or the sham treatment arm [REDACTED]. Participants and clinician assessors will be blinded. For each enrollee's 6-week participation in the study, the participant will be instructed to self-administer [REDACTED]

[REDACTED] and complete daily surveys (self-reports on anxiety levels, medication use, and skin tingling felt during treatment) on the Empower app (on the provided smartphone). Weekly, the participant will be prompted to complete the BAI survey

**Figure 2.** Study outline. This 6-week study will include three study visits. For the duration of the study, participants will self-administer twice daily treatment sessions at home with the Empower Neuromodulation System and complete daily and weekly surveys. At Visits 1 and 2, clinician assessments will be administered and participants will complete surveys. The study completion visit will also include a usability survey and Study Completion Questionnaire.

on the Empower app. At the enrollment visit (Visit 1) and the final study visit (Visit 3), the participant will be assessed by one of the study clinicians for anxiety (HAM-A) and depression (HAM-D). At these study visits, the participant will also complete the following surveys on paper or electronically: PCL-5 GAD-Q-IV, PHQ-9, PSQI, and SF-12. At all clinic visits, the participant will be assessed for suicidality via the Columbia-Suicide Severity Rating Scale-Revised (C-SSRS-R).

Once enrolled and trained on device and app use, the participant will be instructed to conduct treatment sessions and complete surveys [REDACTED]

The Empower Neuromodulation System (which includes a smartphone with

Empower app) will be loaned to each participant for the duration of his/her participation in the study.

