### 9.1.7 Surveys

Throughout the study, the participant will provide responses and complete surveys that cover medication use, skin tingling during treatment, anxiety, depression, sleep quality, and quality of life. Daily surveys (medication use, skin tingling during treatment, anxiety

severity and interference with daily living) and weekly surveys (BAI) will be completed on the Empower app. Surveys will be completed at the same time as Empower treatment (the participant will be guided by the app as to when each survey is to be completed). Surveys conducted at Visits 1 and 3 (GAD-Q-IV, PHQ-9, PSQI, and SF-12) will be completed electronically or on paper. At each clinic visit, the participant will complete the daily and weekly surveys if they have not been completed for that day/week. At the final clinic visit, the participant will also complete the following electronic or paper-based surveys: usability survey (SUS), rating of overall satisfaction with treatment (100-mm VAS), blinding assessment, and a Final Study Questionnaire that includes questions regarding feedback on device features, device comfort and tolerability, and marketing questions.

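### Does the tingling endpoint need a written rule for treatment sessions that have no tingling answer?

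*Combined protocol and SAP*

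**What the plan says.** Section 15.4 computes effective nerve stimulation for each participant as "treatment sessions that elicit skin tingling as a percentage of total treatment sessions", then compares active and sham by t-test. Section 5.2 defines the same endpoint at session level and makes the participant's own confirmation of tingling the evidence.

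On the treatment schedule, the Figure 2 caption in Section 4.4 states that "participants will self-administer twice daily treatment sessions at home".

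On when tingling is asked, the readable text is as follows:

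- Section 4.4 has participants "complete daily surveys (self-reports on anxiety levels, medication use, and skin tingling felt during treatment" on the app.
- Section 9.1.7 lists tingling among the daily items: "Daily surveys (medication use, skin tingling during treatment, anxiety" and so on. It adds that "the participant will be guided by the app as to when each survey is to be completed".
- Section 9.1.7.1 says: "The app will guide the participant to complete the daily survey prior to self-administering the first treatment session of each calendar day". Its next sentence is: "Immediately after the session, the participant will also be asked about anxiety severity at the present time and if a tingling sensation was felt".
- A later sentence in Section 4.4 reads "the participant will be instructed to conduct treatment sessions and complete surveys" and is then redacted. Section 9.1.8, on the treatment session itself, is redacted in full.

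Section 15.3 counts a session as completed once 20 minutes have been given, but states this only for adherence.

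**The concern.** Numerator and denominator come from different sources. The device and app log each session automatically (Sections 4.4 and 8.3), whereas tingling is known only if the participant is asked and answers. If the question appears once a day and treatment is given twice a day, about half the logged sessions have no answer by design. Section 15.4 does not say whether such sessions drop out or count as not effective, so identical behaviour could yield very different percentages.

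Under the second choice the score would also depend on the pattern of sessions. A participant who completes more second sessions would score lower, so this feasibility measure would move against adherence, which is the primary one. If session patterns differed by arm, the t-test could show a difference with no difference in nerve stimulation behind it. This is the only secondary feasibility endpoint, and Section 5.1 ties the evaluation of the feasibility endpoints to finding a suitable sham for a later pivotal study.

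**Working it through.** The plan attaches no target, power or sample size figure to this endpoint, so there is nothing of its own to reproduce. The check is ratio arithmetic.

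**Inputs.** Two sessions a day for 6 weeks (Synopsis, Section 4.4): 6 × 7 × 2 = 84 sessions over 42 days. The ± 7 day window for Visit 3 gives about 35 to 49 days, or 70 to 98 sessions. Assume first that every answer is yes.

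**Case A: asked once daily, both sessions done each day.**

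| Rule for sessions with no answer | 35 days | 42 days | 49 days |
|---|---|---|---|
| Left out | 35/35 = 100% | 42/42 = 100% | 49/49 = 100% |
| Kept as not effective | 35/70 = 50% | 42/84 = 50% | 49/98 = 50% |

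**Case B: asked once daily, some second sessions missed.** Let D be the days with a first session and f the share of those days that also have a second session. With unasked sessions kept as failures and administered sessions as denominator, the ceiling is D/(D + fD) = 1/(1 + f):

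- f = 0: 100%
- f = 0.25: 1/1.25 = 80%
- f = 0.5: 1/1.5 = 66.7%
- f = 0.75: 1/1.75 = 57.1%
- f = 1: 50%

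With answered sessions as denominator the score is 100% throughout. Suppose, purely as an assumption, that f is 0.9 in one arm and 0.6 in the other. The ceilings are 1/1.9 = 52.6% and 1/1.6 = 62.5%, a gap of 9.9 points with no true difference. The documents give no f and nothing that suggests it differs by arm.

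**Case C: asked after every session, a share m of answers skipped.** With skipped answers kept as failures the score is 1 − m: 90% at m = 10% and 80% at m = 20%, against 100% for answered sessions only. The documents give no m.

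**What the 50% needs.** Three conditions must hold together:

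1. The question is asked once daily.
2. Unasked sessions are scored as not effective.
3. The total means sessions administered or scheduled, not sessions asked.

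The first is a fair inference from Sections 4.4, 9.1.7 and 9.1.7.1. It is not established, because Section 9.1.7 leaves timing to the app, Section 5.2 uses session-level wording, and the likely places for the detail are redacted. The second is stated nowhere. The third is open: the literal wording allows it, but does not decide how an unasked session is coded.

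**Whether the obvious repair is free of cost.** Take Case C with m = 10%, and suppose the skipped sessions are exactly those without tingling. The true share is 90%, and the answered-only denominator reports 100%. If the question is asked once daily, that denominator describes only the first session of the day. Neither denominator is right under every way the data may arise.

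**The case for a change.** The strongest case for a change is that Section 15.4 is fully readable and silent, so redaction elsewhere does not excuse it. How often the question is asked may sit in Section 9.1.8, but the rule for missing answers belongs in the analysis section.

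Once-daily asking also has support beyond the survey lists. The post-session prompt pairs tingling with present-time anxiety. The matching pre-session rating sits in the daily survey, which is tied to the first session, and no readable text gives a pre-session rating for the second. A literal analyst could divide yes answers by logged sessions and report about 50% for a device that worked every time. Two or three sentences would prevent that.

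Much of this stands: the silence is real, the once-daily inference is reasonable, and the arithmetic is right. What does not stand is the step to a wrong result. Section 5.2 makes participant confirmation the measure, and treating an unasked session as a failed one is an implausible reading of that. The error would also show itself: if one question a day were divided by two sessions a day, no fully adherent participant could exceed 50%, and an analyst holding the session log and the answers would see why. The proposed wording is itself partly a preference. If every session is asked, counting a skipped answer as not confirmed is a defensible cautious rule, and the answered-only rule can overstate. Nor would an answered-only definition settle whether sessions under 20 minutes count.

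**Conclusion.** No change follows. This is missing detail that an analyst would fill sensibly from the app data. No stated rule has been shown to give a wrong result.

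The largest effect, 50% instead of 100%, is the extreme of a chain of assumptions: once-daily asking, unasked sessions scored as failures, full adherence, and tingling every time. If the question follows every session, the effect shrinks to the share of answers skipped, which the documents do not give. No bias between arms can be claimed, because nothing indicates that session patterns differ by arm. At most one secondary endpoint in a 30-participant pilot is involved. Adherence, SUS and the sample size do not depend on it.

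The conclusion rests on the analyst having both the session log and the answers, as Sections 4.4, 8.3 and 16.4 indicate, and on the final report stating the denominator used.
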